5.2 Secondary outcomes

None available.

5.3 Other Outcomes of Interest

None available.

5.4 Safety Outcomes

No further outcomes are included that serve the purpose of safety.

Discontinuation of the experiment is the responsibility of the examiners with regard to the subject's resilience. If this is judged to be too low, the examiner can stop the experiment.

If the test subject does not feel well according to her own subjective assessment, she can stop the experiment and withdraw participation in the study. If the cold application is unacceptable for the test subject, she can discontinue the application. She will not suffer any disadvantages as a result.

The current regulations of the Canton of Graubünden and those of the FOPH for protection against the coronavirus will be taken into account and implemented when conducting the study.

SUPSI

6. STUDY DESIGN

6.1 General study design and justification of design

Randomized, controlled trial

This is a remaining clinical trial in risk category A (Chapter 4).

The group size of the participants is N = 60 people. Group allocation is randomised.

6.2 Methods of minimising bias

All measurements are carried out and recorded in a standardized manner by the same tester. The laboratory conditions are always the same.

6.2.1 Randomisation

The allocation to the different groups (cold water bath, hot water bath, hypoxia, control group) takes place randomly by drawing of a lot.

6.2.2 Blinding procedures

Blinding the participants is not possible in this study. The investigators are blinded by adding another investigator who operates the apparatus. The responsible statistician is blinded and has no access to the personal data of the test subjects and is not present when the data is collected.

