8.4 Compliance with study intervention

The test subjects are only motivated to perform MVIC and the jump height measurement in order to keep their compliance high. The rest of the communication is kept to a minimum. Only study-related conversations are conducted in order not to influence the psychophysiological effects and to ensure homogeneity.

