Oxygen saturation (blood, muscle) Mod. BORG & BORG =30 min	Oxygen saturation (blood, muscle) Mod. BORG & BORG =30 min	Oxygen saturation (blood, muscle) Mod. BORG & BORG =30 min	Oxygen saturation (blood, muscle) Mod. BORG & BORG =30 min
3.) Cold water immersion 10 min at 10°C Heart rate Skin/core body temperature Oxygen saturation (muscle) Thermal comfort and Temperature sensation =10 min	3.) Hot water immersion 10 min at 40°C Heart rate Skin/core body temperature Oxygen saturation (muscle) Thermal comfort and Temperature sensation =10 min	3.) Passive supine position 10 min at room temperature Heart rate Skin/core body temperature Oxygen saturation (muscle) Thermal comfort and Temperature sensation =10 min	3.) Passive supine position 10 min at room temperature Heart rate Skin/core body temperature Oxygen saturation (muscle) Thermal comfort and Temperature sensation =10 min
4.) Follow-up immediately after the intervention Heart rate Skin/core body temperature Oxygen saturation (blood, muscle) Inflammation parameters US VAS & BORG 3 x Vertical Jumps 3 x MVIC =30 min	4.) Follow-up immediately after the intervention Heart rate Skin/core body temperature Oxygen saturation (blood, muscle) Inflammation parameters US VAS & BORG 3 x Vertical Jumps 3 x MVIC =30 min	4.) Follow-up immediately after the intervention Heart rate Skin/core body temperature Oxygen saturation (blood, muscle) Inflammation parameters US VAS & BORG 3 x Vertical Jumps 3 x MVIC =30 min	4.) Follow-up immediately after the intervention Heart rate Skin/core body temperature Oxygen saturation (blood, muscle) Inflammation parameters US VAS & BORG 3 x Vertical Jumps 3 x MVIC =30 min

SUPSI

5.) Cold water immersion 10 min at 10°C Heart rate Skin/core body temperature Oxygen saturation (muscle) Thermal comfort and thermal sensation =10 min	5.) Hot water immersion 10 min at 40°C Heart rate Skin/core body temperature Oxygen saturation (muscle) Thermal comfort and thermal sensation =10 min		

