12.2 Data management

12.2.1 Data Management System

The raw data of muscle activity is processed using OT Bioelettronica's (MISO II) software. The oxygen measurement data is acquired with the research software "moorFLPI-2 full-field laser Perfusion Imager V1.1". The jump height is determined with a jump height measuring plate designed for this purpose (Just Jump Plate, Probotics Inc., Huntsville, USA). The data from the thermal imaging camera is processed with the "Flir Research IR max" software. The inflammation parameters are recorded with the Reflotron (Roche Diagnostic, Rotkreuz, Switzerland) and transferred to a data sheet. Dyspnea and stress assessment are recorded in writing with a questionnaire. The subjective sensation parameters regarding thermal comfort and temperature perception are asked verbally and the answers are transferred by hand to the raw data sheet. Excel is used for further data analysis. Windows® Excel will also be used for data pooling and for the graphical visualisation of the final data. The skin temperature is measured via the iButton system and stored on the PC using the software provided (iButton MMT). To assess muscle swelling, the MyLabClassC ultrasound is used (Esaote, Genoa, Italy). The images are then analysed using the OsiriX DICOM viewer software (OsiriX, Pixmeo SARL, Switzerland). Blood oxygen saturation is measured with a portable pulse oximeter with finger clip probe (Nonin 7500, Nonin medical B.V., Plymouth, USA) and transferred directly to a Windows® Excel template. The data from the core body temperature measurement is transmitted wirelessly to a monitor (BodyCAP medical, Hérouville Saint-Clair, France) and recorded.

All data is processed on the central research computer. This research computer is located in Landquart (research laboratory) at all times. Only the principal investigator and the investigators (listed in Chapter 1) know the password to unlock this computer. All digital documents are write-protected by a password. Only the study director and the examiners know the passwords of the digital documents. The digital documents are given a version number. Any changes made to the digital documents are saved as a new version number. In addition, all versions will be printed out and signed by the study director. The printed documents are stored in a separate, lockable filing cabinet. This filing cabinet also contains the password

SUPSI

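### The investigator blinding claimed in section 6.2.2 does not hold as written: one tester takes all measurements, including those made during the baths

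*Combined protocol and SAP*

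**What the plan says.** Section 6.2.2 concedes that "Blinding the participants is not possible in this study". It then claims masking on the staff side: "The investigators are blinded by adding another investigator who operates the apparatus". It also describes the statistician as blinded and absent from data collection.

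Section 6.2 states: "All measurements are carried out and recorded in a standardized manner by the same tester".

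The flow chart in section 9.1 lists, for the cold group, "3.) Cold water immersion 10 min at 10°C Heart rate Skin/core body temperature Oxygen saturation (muscle) Thermal comfort and Temperature sensation =10 min" and, for the hot group, "3.) Hot water immersion 10 min at 40°C Heart rate Skin/core body temperature Oxygen saturation (muscle) Thermal comfort and Temperature sensation =10 min". The bath groups repeat these readings in a second bath (step 5). The hypoxia and control groups have the same step 3 readings while supine. Step 2 schedules readings around the jump protocol, which the hypoxia group performs under hypoxia.

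Section 12.2.1 says how the thermal ratings are obtained: "The subjective sensation parameters regarding thermal comfort and temperature perception are asked verbally and the answers are transferred by hand to the raw data sheet". Section 9.2.1 has the skin sensors taken off for the bath and put back afterwards.

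Section 8.4 says: "The test subjects are only motivated to perform MVIC and the jump height measurement in order to keep their compliance high". Section 4.2 lists jump height, MVIC and muscle swelling among the primary measurements.

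**The concern.** Having a colleague run the apparatus hides the arm only from someone who is not there when the apparatus is in use. The plan schedules readings at exactly that time and gives all readings to one person. If that person also runs the later jump, MVIC and ultrasound tests, those tests are not blinded.

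Two things are at stake. First, an assessor who knows the arm can encourage or handle participants differently in tests that depend on effort, or acquire ultrasound images differently, and so create or distort a difference between groups. Second, a report that follows section 6.2.2 would claim a safeguard that was not in place.

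**Working it through.** The plan gives no figure on this point, so the check is a reading of the sections side by side.

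1. **Who measures.** Section 6.2: one tester, all measurements. The only stated exception is the blood measurement, which section 9.2.1 gives to trained specialists. No exception is made for jump height, MVIC or ultrasound.
2. **When.** Section 9.1, steps 3 and 5: readings fall within the 10-minute bath.
3. **Whether those readings need someone present.** The chest strap, wireless skin sensors and capsule could be read remotely. The thermal ratings cannot, because section 12.2.1 has them asked aloud and written down by hand. Removing and reattaching the skin sensors also needs someone at the bath.
4. **Consequence for the bath groups.** From 1 to 3, the tester sees whether the participant is in cold water, in hot water or supine before the step 4 tests and the 24, 48 and 72 h tests.
5. **Consequence for hypoxia against control.** Both groups lie supine in step 3, so that step does not separate them. They differ in step 2, where readings are also taken and no sham hypoxia device is described. Disclosure is likely there, but the inference is weaker than for the baths.
6. **The code-break text.** Section 6.3 sets conditions for unblinding investigators and participants. Section 6.2.2 says participants cannot be blinded, so that part of section 6.3 has nothing to act on.
7. **Route to bias.** The jump plate and the ergometer chair give instrument readings, so misreading is a minor route. Effort is the main one: participants are motivated for precisely these two tests, and no standard wording is described. Ultrasound depends on the operator.

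**Scale, by assumption only.** Suppose there is no true effect and knowledge of the arm shifts one outcome by δ SD in one group. For a two-sided 5% two-sample t-test with n per group, the non-centrality is δ√(n/2) on 2n − 2 degrees of freedom. The totals of 40 (section 11.2) and 60 (section 6.1), split equally over four groups, give n = 10 and n = 15.

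| δ (assumed) | Non-centrality, n = 10 | False-positive rate, n = 10 | Non-centrality, n = 15 | False-positive rate, n = 15 |
|---|---|---|---|---|
| 0.2 | 0.447 | 7.1% | 0.548 | 8.3% |
| 0.3 | 0.671 | 9.7% | 0.822 | 12.5% |
| 0.4 | 0.894 | 13.5% | 1.095 | 18.5% |

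These figures show sensitivity and do not estimate the bias. The values of δ are not in the documents, and the planned analysis is a four-group repeated-measures model, not a single t-test.

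**The case against.** The best counter-argument is that section 6.2 may only mean a consistent rater for each test, with the second investigator covering the bath phase. The blood exception shows that the single-tester sentence is not fully literal, and section 8.2.1 puts an examiner beside the participant without saying which one. This may be what the sponsor intends. But no section assigns the in-bath readings to the second investigator, and section 6.2 as written says the opposite. If that is the intent, it needs to be written down.

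The plan also has real mitigations. Measurement is standardised, dialogue is kept to a minimum (sections 6.2.3 and 8.4), and the statistician is masked. They reduce the room for bias, but they do not make the tester blind.

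A reader might go further in three ways that the documents do not support:

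- **That section 8.4 shows the unblinded tester giving verbal encouragement.** The sentence is passive, names nobody and does not say the motivation is verbal.
- **That soreness is biased by the tester.** Soreness is self-reported by participants who know their arm. Most of that bias would remain whoever holds the form.
- **That the inflation in the table is the expected damage.** The shift is wholly assumed.

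It is also fair to say that unblinded participants limit what assessor masking can achieve. That does not justify leaving a second, avoidable source of bias, or an inaccurate claim, in the protocol.

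**Conclusion.** Wrong as written. Sections 6.2 and 9.1 together make the investigator blinding of section 6.2.2 unattainable for the person who measures jump height, MVIC and ultrasound swelling. This is firm for the bath groups and probable for hypoxia against control. It rests on taking the single-tester sentence at face value; nowhere do the documents say outright that the tester knows the arm. The direction and size of any resulting bias cannot be determined from the documents. Participant-side bias, including in soreness, remains in any case. The point should be corrected because it concerns a stated safeguard on primary outcomes and most of the remedy is a matter of assigning tasks.

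**What to change.** Reconcile sections 6.2, 6.2.2, 6.3 and 9.1 as follows.

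- **Steps 2, 3 and 5:** assign the readings to the apparatus investigator and other examiners already listed in the synopsis, keeping the two examiners whom section 3.7 places beside the participant during jumping.
- **Outcome tester:** name one person who is absent from steps 2, 3 and 5 and has no access to those data. This person does baseline before the lot is opened, and the jump, MVIC and ultrasound tests at 24, 48 and 72 h.
- **Step 4:** let the same tester do the jump, MVIC and ultrasound tests here too, so that the rater does not change across the Time factor of section 11.4.2. State that step 4 may not be masked. Because step 4 precedes the second bath, also state that masking at 24 to 72 h may then be only partial.
- **Conduct:** use standardised encouragement, and ask participants not to reveal their arm.
- **Wording:** in section 6.2, specify the same tester for each measurement. In section 6.3, drop the provisions for unblinding participants.

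If this is not done, say plainly that outcome assessment is unblinded and that only the statistician is masked.

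The cost is reassigning people already on the study and a few sentences of text; sample size, outcomes and interventions do not change. The downsides are that more than one person takes day-0 readings and that masking stays partial.

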6.2.3 Other methods of minimising bias

The content of the dialogue between the test subjects and the examiner is kept to a minimum.

6.3 Unblinding Procedures (Code break)

There is no provision for cancelling the statistician's blindness.

Unblinding of the investigators and/or the study participants is only permitted if an unforeseen event or medical problems occur during or after completion of the study participation in a subject which may be attributable to participation in the study.

In the event of adverse events (AEs) occurring during or shortly after study participation that may be attributable to the intervention, the principal investigator may, at his or her discretion, immediately unblind the study participant and the attending investigators to ensure adequate treatment of the study participant.

In the case of incidents (AE) that occur for longer than 24 hours, clarification by a doctor is mandatory and a medical certificate is required for the cancellation of the blindness. Data may then also be passed on to the attending physician with the consent of the study participant concerned. This approach is justified, as no life-threatening incidents are to be expected as a result of the interventions used here.

SUPSI

7. STUDY POPULATION

7.1 Eligibility criteria

Inclusion criteria

- Young healthy women aged 18 - 35 years
- No surgical interventions on the musculoskeletal system in the trunk area and on the lower extremities
- Anticonceptives

Exclusion criteria

- Current injuries of any kind affecting the trunk and/ or lower extremities
- Injuries to the trunk and/ or lower extremities that occurred less than 1 year ago
- Injuries to the trunk and/ or lower extremities that occurred more than 1 year ago and are still causing symptoms
- Fear of cold and/or hot water intervention
- Fear of hypoxia
- Taking medication of any kind (including self-purchased medication)
- Pacemakers & cardiac arrhythmias
- Known circulatory problems
- Positive pregnancy test
- Diagnosed skeletal static deviations
- Appendectomy less than 2 years ago
- Raynaud's syndrome

To our knowledge, only a few studies have so far investigated the physiological response or recovery after a hot/ cold water bath, hypoxia and control treatment in women. This is consistent with the significantly underrepresented female participation in the wider sports and exercise medicine literature (Costello et al. 2014). In addition, a recent Cochrane review on whole-body cryotherapy concluded that the existing literature on cryotherapy may not be applicable to women and warrants future research on female participants in this area (Costello et al. 2015). In addition, the altered hormone status during the female cycle (e.g., estrogen) and anthropometric differences (e.g., fat distribution and total body fat) could lead to differences according to a muscle-damaging protocol in women.

7.2 Recruitment and screening

Recruitment

It is published on the website (homepage & Facebook) of Thim van der Laan University College Physiotherapy and the University of Applied Sciences and Arts of Southern Switzerland (SUPSI). The exact texts have been prepared according to the checklist of the Cantonal Ethics Commission Zurich.

SUPSI

As advertisements (text visible):

- Homepage of the Thim van der Laan School of Physiotherapy: www.physioschule.ch and SUPSI: www.supsi.ch
- Facebook page of the Thim van der Laan Physiotherapy School: <https://www.facebook.com/physioschule> and SUPSI: <https://www.facebook.com/supsi.physiotherapie/>

Screening

During the initial contact, the potential participants are informed about the procedures and risks of the study, as well as its conditions and the amount of compensation. A checklist for contacting them by telephone serves as a basis.

During the first telephone contact, a questionnaire to determine the suitability as a study participant is completed by the study management. In advance, it is explained to the subject that answering the questions is voluntary and can be interrupted at any time and that all registered information will be deleted immediately if they decide not to participate in the study.

Advertisements, questionnaires and checklists for the first contact can be found in the enclosure.

7.3 Assignment to study groups

Group allocation is carried out secretly with the help of a ticket in a sealed envelope, which is drawn under the supervision of the study director. This lot indicates whether the test subject is undergoing the cold water bath, hot water bath, hypoxia or control intervention.

7.4 Criteria for withdrawal / discontinuation of participants

If a participant withdraws from the study, the allocation lot is returned to the pot in a new envelope and a new participant is sought.

The already completed consent form is kept in the locked filing cabinet. If consent is withdrawn, the data and samples already collected must be included in the analysis for scientific and safety reasons. These will only be anonymised after the analysis (Art. 9 ClinO).

The conditions for discontinuing the trial were described in chap. 5.4. There is no disadvantage for the participants if they discontinue their participation in the study.

SUPSI

8. STUDY INTERVENTION

8.1 Identity of Investigational Products (treatment / medical device)

8.1.1 Experimental Intervention (treatment / medical device)

Both application devices (Cloud9 and Whirlpool Aspen) are certified products.

Whirlpool Aspen

The Aspen Whirlpool is an inflatable water pool with four seats and a capacity of 700l. The heating of the 168cm x 168cm whirlpool can be adjusted up to 42°C. The water filtration runs automatically. The CE marking indicates that the product meets the essential requirements of the European Directives 2006/95/EC (Low Voltage), 2004/108/EC (electromagnetic compatibility) 2011/65/EU (restriction of the use of certain substances in appliances e) 2009/125/EC (ecodesign of energy-related products).

Securing the test subjects

Only subjects who have completed the health questionnaire without risk factors will be admitted to the study. In this way, risk factors are recognised at an early stage and the subjects for the study are not recruited.

The examiner is in direct contact with the subject at all times. The examiner is at eye level with the test subject and monitors the procedure. With their signed consent form, the test subjects declare that they have already taken a pregnancy test (urine test). This test is handed out, collected and interpreted by the head of the study. Only the principal investigator, the study supervisor and authorized employees of the CEC can view this test result. The thermo- or hypoxia application can be discontinued by the investigator at any time. If the thermal or hypoxia application is perceived as unpleasant by the test subjects, they can cancel the application at any time. Therefore, there is only a minimal risk for the test subjects. Furthermore, a fully functional and annually maintained defibrillator is available at the time of the study. All research staff and investigators can operate this defibrillator and have the competence of "first aid" measures. For these reasons, the presence of a doctor is not required. The test subjects are only allowed to enter the interventions without metal body jewellery (no piercings, rings, necklaces, etc.). Furthermore, the test subjects are advised to refrain from skin creams or other skin cosmetics. This is also evident in the subject information.

8.1.2 Control Intervention (standard/routine/comparator treatment / medical device)

Hypoxia group

With the Cloud 9, a simulated altitude of 2700 m above sea level and 4000 m above sea level can be achieved. This corresponds to an oxygen partial pressure of 15.0% and 12.7% respectively. The Cloud 9 altitude training device is intended for anyone (including amateurs) who wants to improve their performance. The Cloud 9 is a solid, certified product that complies with the European Directives on electromagnetic compatibility, Machinery Directive, air pressure equipment and low voltage equipment (89/336/EEC, 91/368/CEE, 93/68/CEE, 97/23/EC, EN61010-1).

Control group

The control group will lie on their backs for 10 minutes after the jump protocol.

8.1.3 Packaging, Labelling and Supply (re-supply)

The Whirlpool Aspen from NetSpa complies with European directives (2006/95/EC, 2004/108/EC, 2011/65/EU, 2009/125/EC). The Cloud 9 is a certified product according to European directives (89/336/EEC, 91/368/CEE, 93/68/CEE, 97/23/EC, EN61010-1).

SUPSI

8.1.4 Storage Conditions

The whirlpools are kept in a room at room temperature and low humidity all year round. The room in which the whirlpools are located is fully ventilated and has the following dimensions: 7m x 14m x 2.5m and thus complies with the specifications in the operating manual.

The Cloud 9 can be stored both outside in the dry and inside a room. The equipment is located inside our laboratory for the duration of the measurements and is only accessible to laboratory staff.

